## 2 Protocol Summary

OBJECTIVE	
Primary Objective  Examine the protection against any type of COVID-19 infection as confirmed by PCR testing or positive serology for N antigen during the follow up period.
 
Secondary Objectives  Evaluate the impact of a fourth dose on:
 
 
1. Symptomatic COVID 19 infection
 
2. COVID 19 infection requiring hospitalization
 
3. Antibody levels including IgG, IgA, IgM, binding and neutralizing activity and the avidity of the antibodies.
 

STUDY DESIGN	Prospective observational registry
OUTCOMES	
Primary Outcome  COVID-19 infection as confirmed by PCR testing or positive serology for N antigen during the follow up period. We hypothesize that booster of BNT162b2 vaccine in healthcare workers (HCW) will lower the rates of the COVID-19 infection as compared to HCW choosing not to receive the second booster.
 
Secondary Outcomes
 
 
1. Symptomatic COVID 19 infection
 
2. COVID 19 infection requiring hospitalization
 
3. Levels of binding and neutralizing activity and avidity of the antibodies
 
4. Composite endpoint of serious adverse events during 14 days following the booster vaccination
 

SAMPLE SIZE CONSIDERATIONS	
We aim to enroll up to 1000 subjects. The following assumptions were used to estimate the power of the analysis.
 
 
• The proportion of the HCW choosing to receive the second booster is 60%
 
• The expected monthly infection rate of 2.5% in the non-vaccinated group
 
• Expected monthly infection rate of 1.0% in the treatment group
 
• Median follow-up until switching to the booster administration in the non-vaccinated group (15%) of 4 months
 
• Type I error (<math>\alpha</math>) = 0.025 (one-sided)
 
• Log-rank test
 
• Enrollment period of 1 month
 
• Lost to follow-up of 10%
 
 
An evaluable sample size of 1000 subjects provides 80.0% power to reject the null hypothesis, signifying the booster strategy is superior to the comparison group at 6 months post-vaccination.

INCLUSION CRITERIA	
 
1. Able to provide written informed consent.
 
2. Healthcare worker in one of the Clalit Health Services Medical centers and is at least 18 years of age.
 
3. Completed three doses of BNT162b2 according to MOH guidelines.
 
4. Third dose was given at least 4 months prior to enrollment.
 

EXCLUSION CRITERIA	
 
1. History of COVID-19 infection.
 
2. History of being treated or is currently being treated for any type of Malignancies or other co-morbid conditions that may result in protocol non-compliance.
 
3. Currently or in the past three months was treated with any type of Immune suppression medication (including chemotherapy, immunomodulatory drugs, biological agents that affect the immune system, any immunosuppressive drug such as corticosteroids).
 
4. Received in the past 4 months monoclonal antibodies of any type.
 

STUDY PROCEDURES	
Screening and Enrollment
 
The following will take place at this visit:
 
 
• Confirmation of eligibility and informed consent will be signed.
 
• Demographics and medical history will be recorded.
 
• COVID-19 questionnaire regarding exposure and symptoms.
 
• Blood draw of three 5 ml vials, for antibody testing.
 
• Blood drawn for PBMC and antibody testing: 
 
◦ Will be ONLY at Soroka Medical Center.
 
◦ 150 subjects will be selected randomly. Subjects participating in this part will have 30 ml (3 vials of 9 ml and 1 vial of 3 ml) of blood drawn for PBMC and antibody testing. Others will have blood draw of three 5 ml vials, for antibody testing.
 
 
 
• A nasal and mouth swab will be performed for IgA, IgG and IgM levels testing
 
 
Visit 2 –6
 
 
• COVID-19 questionnaire regarding exposure and symptoms. Blood draw of 3 vials of 5 ml for antibody testing,
 
• Blood drawn for PBMC and antibody testing: 
 
◦ Will be ONLY at Soroka Medical Center. Subjects who were not part of the PBMC group and are willing to participate, will be asked again to sign informed consent.
 
◦ Subjects participating in this part will have 30 ml (3 vials of 9 ml and 1 vial of 3 ml) of blood drawn for PBMC and antibody testing. Others will have blood draw of three 5 ml vials, for antibody testing.
 
 
 
• A nasal and mouth swab will be performed for IgA, IgG and IgM levels testing
 
• Adverse events following vaccination and changes in medications (chronic and/or Immune suppression medication) will be collected
 

LABORATORY TESTING	
 
From each HCW at each visit the following tests will be performed:
 
The Platelia SARS-CoV-2 Total Ab assay by Bio rad, is a semi-quantitative in vitro diagnostic test, in a one-step antigen capture format, for the detection of IgM/IgA/IgG antibodies to the SARS-CoV-2 in human serum and plasma (EDTA, heparin, ACD or citrate) specimens. This assay will be performed at SMC virology laboratory (head-[name]).
 
Antibody profiling of blood and nasal samples will be tested using antigen microarrays, this will be performed by using chip antigen microarrays spotted with various coronavirus antigens, as well as antigens of other common respiratory pathogens. This assay will be performed at [name] laboratory at Ben-Gurion University of the Negev.
 
On select samples from each visit neutralization assays for SARS-CoV-2 virus variants will be performed. Each sample selected will be tested for its ability to inhibit infection of target ACE2-expressing cells by reporter pseudoviruses that express the spike protein of either Delta or Omicron Variant of Concern. This assay will be performed at [name] laboratory at Ben-Gurion University of the Negev.
 
Blood samples for PBMC'S will be stored at [name] laboratory at Ben-Gurion University of the Negev for future research.
 

DATA TO CAPTURE	
The following data will be collected:
 
 
Demographic data: age, sex, country of birth, healthcare profession, direct contact with covid subjects in working capacity.
 
Detailed medical history, including but not limited to past illness with COVID, malignancy, diabetes, renal failure, heart disease, hypertension, history of stroke, rheumatological illness.
 
Current medications used and medications used for more than one week in the past three months.
 
Any adverse event during the study as a result of vaccination.
 

DATA MANAGEMENT AND ANALYSIS	
The study will be overseen and managed by the Soroka Clinical Research Center.

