### 5.3 Schedule of Events

Visit number		1	2	3	4	5	6
Time point ( $\pm$ 2 week)	Enrollment	Month 1	Month 2	Month 3	Month 4	Month 5	Month 6
Informed Consent	X						
Inclusion/Exclusion Criteria	X						
Demographics and Medical History	X						
Blood samples*	X	X	X	X	X	X	X
Nasal and mouth Swab**	X	X	X	X	X	X	X
Questionnaire	X	X	X	X	X	X	X
Adverse events	X	X	X	X	X	X	X

\* Antibody levels including IgG, IgA, IgM, binding and neutralizing activity and the avidity of the antibodies. Serum separation and freezing at each site. Only at Soroka medical blood will be drawn for PBMC testing in addition to antibodies testing.

\*\* Antibody levels including IgG, IgA, IgM

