### **5.8.2 Visit 2 –6**

- COVID-19 questionnaire regarding exposure and symptoms. Blood draw of three vials of 5 ml for antibody testing,
- Blood drawn for PBMC and antibody testing:
  - Will be at ONLY at Soroka Medical Center. Subjects who were not part of the PBMC group and are willing to participate, will be asked again to sign informed consent.
  - Subjects participating in this part will have 30 ml (3 vials of 9 ml and 1 vial of 3 ml) of blood drawn for PBMC and antibody testing. Others will have blood draw of three 5 ml vials, for antibody testing.
- A nasal and mouth swab will be performed.
- Adverse events following vaccination and changes in medications (chronic and/or Immune suppression medication) will be collected

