### 5.11.2 Data Collection

The final set of CRFs is designed to accommodate the specific features of the trial design. Modification of CRFs will only be made if deemed necessary by Soroka CRC. The CRFs will be filled out manually by the study personal and or will be collected through the computer services database.

The following data will be collected:

- Demographic data: age, sex, country of birth, healthcare profession, direct contact with covid subjects in working capacity.
- Detailed medical history, including but not limited to past illness with COVID, malignancy, diabetes, renal failure, heart disease, hypertension, history of stroke, rheumatological illness.
- Current medications used and medications used for more than one week in the past three months.
- Any adverse event during the study as a result of vaccination.

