## 6 Statistical Considerations and Analysis Plan

In this prospective observational registry we aim to assess the rates of the COVID-19 infection as confirmed by PCR testing or positive serology for N antigen during the follow up period. We hypothesize that booster of BNT162b2 vaccine in healthcare workers (HCW) will lower the rates of the COVID-19 infection as compared to HCW choosing not to receive the second booster.

We aim to enroll up to 1000 subjects. The following assumptions were used to estimate the power of the analysis.

- The proportion of the HCW choosing to receive the second booster is 60%
- The expected monthly infection rate of 2.5% in the non-vaccinated group
- Expected monthly infection rate of 1.0% in the treatment group
- Median follow-up until switching to the booster administration in the non-vaccinated group (15%) of 4 months
- Type I error ( $\alpha$ ) = 0.025 (one-sided)
- Log-rank test
- Enrollment period of 1 month
- Lost to follow-up of 10%

An evaluable sample size of 1000 subjects provides 80.0% power to reject the null hypothesis, signifying the booster strategy is superior to the comparison group at 6 months post-vaccination.

All statistical analyses will be performed using Statistical Analysis System (SAS) for Windows (version 9.4 or higher, SAS Institute Inc. Cary, NC) or other widely accepted statistical or graphical software. In general, data for all study patients will be combined and presented. Individual data will be presented in patient listings.

Descriptive statistics will be used to present the data and to summarize the results. Categorical variables will be presented using frequency distributions and cross tabulations with numbers and percent per group. Continuous variables will be summarized by presenting the number of observations (N), mean, 95% confidence interval of the mean, standard deviation, median, minimum, and maximum values.

The primary outcome will be analyzed within the paradigm of the survival analysis, i.e. log-rank test for the univariate analysis. Since it is possible that those who chose not to be vaccinated will differ in a number of characteristics, we will utilize Cox regression models with time dependent variable (timing of the booster) with the adjustment for the potential confounders. The confounders will be identified by the DAG approach. In addition different approaches to approximate the counterfactual world assumption such as propensity score adjustment will be considered.

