## 7 Adverse Events

### 7.1 Adverse Event Definition

#### 7.1.1 Adverse Event

Any undesirable experience (sign, symptom, illness, abnormal laboratory value, or other medical event) occurring to a subject, that is considered related to the investigational treatment regimen prescribed as part of the clinical protocol, predefined in the clinical protocol and/or Instructions For Use, that is identified or worsens during a clinical study.

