#### 7.1.3 Serious Adverse Event

A serious adverse event as one when the subject outcome is one of the following: Death, Life-threatening, Hospitalization (initial or prolonged), Disability - significant, persistent, or permanent change, impairment, damage or disruption in the subject's body function/structure, physical activities or quality of life, Congenital anomaly or requires intervention to prevent permanent impairment or damage.

Since this is an observational registry study, SAEs will not be reported to the EC, but will be included in the statistical analysis.

All side effects as a result of vaccination will be reported to Ministry of Health.

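### The only safety outcome exists solely in the 14 days after the booster, so it has no reference rate, and the protocol conflicts on which serious events are recorded

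*Protocol*

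**What the plan says.** Section 2 lists four secondary outcomes. The fourth is the "Composite endpoint of serious adverse events during 14 days following the booster vaccination". It is the only safety outcome, and neither section 2 nor section 5.2.2 states a safety objective. No index date, control window or reference period is given for workers who do not take the booster.

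On which events are recorded, the protocol speaks in two ways.

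- **Broad.** Section 7.1.3 works from the result of the event ("A serious adverse event as one when the subject outcome is one of the following", followed by death, hospitalization and so on) and has no relatedness wording of its own. It adds that "SAEs will not be reported to the EC, but will be included in the statistical analysis". The schedule in section 5.3 has a row "Adverse events" marked at enrollment and at every month, not split by booster status.
- **Narrow.** Section 5.8.2 says "Adverse events following vaccination and changes in medications (chronic and/or Immune suppression medication) will be collected". Section 5.11.2 lists among the data to capture "Any adverse event during the study as a result of vaccination". Section 7.1.1 confines an adverse event to one "that is considered related to the investigational treatment regimen prescribed as part of the clinical protocol".

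**The concern.** A window that opens at the booster has no counterpart in someone who is never boosted. The study has a concurrent unboosted group, but this outcome does not use it. A small number of serious events in the 14 days could be ordinary background or a booster effect, and the outcome as defined gives no means of telling which.

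The conflict over recording makes this more than a question of analysis. A missing comparator could be supplied later in a statistical analysis plan, but only if serious events in unboosted time, and in boosted time outside the 14 days, have been recorded. Sites that follow the narrow wording will not record them.

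**Working it through.** The protocol gives no expected rate, precision or power for this outcome, so there is no stated figure to reproduce. Its one power figure concerns the infection comparison and has no bearing here.

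**Inputs from the protocol (sections 5.10 and 6).** Up to 1000 subjects; 60% boosted, so 600 boosted and 400 not; 6 months of follow-up; 15% of the unboosted switching; infection rates of 1.0% (boosted) and 2.5% (unboosted) per month.

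**Assumption.** The protocol gives no background rate of serious events. I use 3, 5 and 10 per 100 person-years, and 2 to 10 for power.

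**Reading 1: section 7.1.3 governs, and events count by outcome.**

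Time at risk: 600 × 14 / 365.25 = 23.0 person-years. Expected events with no booster effect are 23.0 × rate, and the chance of at least one is 1 − exp(−expected):

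| Assumed rate per 100 person-years | Expected events | Chance of at least one |
|---|---|---|
| 3 | 0.69 | 50% |
| 5 | 1.15 | 68% |
| 10 | 2.30 | 90% |

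Adding switchers (15% of 400 = 60, so 660 boosted) gives 25.3 person-years and 0.76 to 2.5 expected events over the same range, so the picture does not change.

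COVID-19 admissions in the window would also count here and again under secondary outcome 2. The overlap is small. At 1.0% to 2.5% per month, 600 workers have about 2.8 to 6.9 infections in 14 days. If 1% to 5% were admitted (an assumption), that is 0.03 to 0.35 admissions.

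**Reading 2: sections 5.11.2 and 7.1.1 govern, and only related events count.**

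Most background admissions drop out, but through a causality judgement made knowing that the worker was boosted. Unboosted workers contribute essentially nothing, so no reference rate can be built afterwards.

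**What a reference would add if all serious events were recorded.**

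- Unboosted time: 400 × 0.5 = 200 person-years before switching and loss, or about 170 with a 15% reduction (200 × 0.85). That is 7 to 9 times the 23.0 person-years at risk. At 2 to 10 per 100 person-years it supplies about 3 (170 × 0.02 = 3.4) to 20 (200 × 0.10) reference events.
- A matched 14-day window in 400 unboosted workers: 400 × 14 / 365.25 = 15.3 person-years, supplying only 0.3 to 1.5 events.
- Boosted time after day 14, if boosted at enrollment: 600 × (182.6 − 14) / 365.25 = 277 person-years before loss.

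Power for a true threefold rate against 170 unboosted person-years was simulated with Poisson counts. The test was a conditional binomial test at one-sided 0.025, with null share 23.0 / (23.0 + 170) = 0.119. Power was 9% at 2 per 100 person-years and 51% at 10. With the matched 14-day control window (two-proportion test, two-sided 0.05) it was 6% to 23%.

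**The case against.** The strongest reply has four parts.

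1. **Serious events are ordinarily a subset of adverse events.** Section 7.1.1 requires relatedness, so background and COVID-19 admissions may never enter the count. This stands in part. A reader might infer that 7.1.3 counts every death or admission whatever its cause, but the protocol does not say so, and 5.11.2 and 7.1.1 point the other way. What remains is a conflict that leaves the count undefined, with a different problem on each reading.
2. **The analysis plan may name a comparator.** True, and the absence of a method in the protocol would not be a finding by itself. But a plan cannot recover events that were not recorded. For the same reason, one might infer from the schedule row that comparison data are nearly in hand; the narrow wording in 5.8.2, 5.11.2 and 7.1.1 does not support that.
3. **A post-dose incidence is a legitimate descriptive outcome, and no safety hypothesis is stated.** This stands. Zero events in 600 would give a one-sided 95% upper bound of 1 − 0.05^(1/600) = 0.50%. It is therefore too strong to say that the outcome answers no safety question. Nor is the general sentence in section 6, "Categorical variables will be presented using frequency distributions and cross tabulations with numbers and percent per group", a contradiction; it is standard descriptive wording.
4. **A comparison would have little power.** This also stands. It is a reason to report an estimate with its interval rather than a test.

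**Conclusion.** The concern holds in this form. Secondary outcome 4 has no value in unboosted workers and no reference rate, and the protocol conflicts on which serious events are recorded. On the broad reading, 0.7 to 2.3 events are expected with no booster effect, so one to three observed events could not be interpreted. On the narrow reading, the count depends on attribution made with knowledge of booster status, and the means of building a reference are lost at collection. The raw proportion remains a valid description but can neither show nor exclude an excess.

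The sizes rest on assumed background rates; the structural point does not. As this is a secondary outcome, it should be corrected, ideally before collection starts, but it does not threaten the primary comparison.

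**What to change.** 1. **Reconcile sections 5.3, 5.8.2, 5.11.2, 7.1.1 and 7.1.3** so that every serious adverse event is recorded in every subject at the existing visits, with its date and regardless of attribution. Attribution can be kept as a separate item.
2. **Redefine secondary outcome 4** as the serious-event rate in the 14 days after the booster, compared with unboosted person-time over the same calendar period. Time before the booster in workers who later switch belongs to the unboosted side.
3. **Add a supporting within-person comparison** of non-fatal events against a later window of exactly equal length in the same boosted workers. For example, counting the booster day as day 1, days 1 to 14 against days 29 to 42 are 14 days each.
4. **Report with and without COVID-19 admissions**, as a rate ratio or difference with its interval, next to the raw proportion.

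Cost: protocol wording, slightly more data recording and a small analysis, with no added visits or subjects. Limits: events will be few and the ratio imprecise. The controls are self-selected, which is why the within-person comparison is added. That comparison cannot handle deaths, and workers boosted in the last six weeks of follow-up will lack a complete later window.

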### 3 Abbreviations and Definitions

Abbreviation	Term
AE	Adverse Event
COVID-19	Corona Virus Disease
CRF	Case report form
EC	Ethics Committee
EOS	End of Study
HCW	Health care worker of clalit health care
IgG	Immunoglobulin G
IgM	Immunoglobulin M
MOH	Ministry of Health
PBMC	Peripheral blood mononuclear cell
PCR	Polymerase chain reaction
SAE	Serious adverse event
SARS-CoV-2	Severe acute respiratory syndrome- corona Virus-2
SMC	Soroka Medical Center
Soroka CRC	Soroka Clinical Research Center

#### **4      Background**

The SARS-CoV-2 virus causes severe respiratory illness and is an ongoing global pandemic. On December 12, 2020 the FDA approved Pfizer's BioNTech vaccine BNT162b2 which is a messenger RNA type of vaccine for use. This vaccine has shown in numerus studies the ability to induce a strong immune response and provide both humeral and cellular protection against wild type, alpha and delta variants of SARS-CoV2 virus. In Israel the national vaccine operation began in mid-December 2020 which included 2 initial doses three weeks apart. In August 2021 a first booster (3rd dose) was provided to enhance protection and due to reports of reduced immune response and clinical protection. Several studies have demonstrated that over time there is a decay in the antibody levels, and with them reduced protection.

Recently a new variant of concern has been identified (Omicron) and is causing a surge of infections worldwide. There is lack of knowledge regarding the effectiveness of the current schedule of vaccine against this new variant and whether a second booster (4th dose) will provide higher levels of clinical protection against this variant, currently the ministry of health is considering recommendations for a fourth dose for HCW.

The purpose of this study is to examine whether a fourth dose of vaccination will provide better protection against infection and clinical disease.

## 5 Methods

### 5.1 Working Hypothesis

In HCW, receiving a second booster (fourth dose) of BNT162b2 vaccine will lower the rates of the COVID-19 infection compared to controls.

### 5.2 Objectives

#### 5.2.1 Primary Objective

Examine the protection against any type of COVID-19 infection as confirmed by PCR testing or positive serology for N antigen during the follow up period.

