### 5.5.2 Exclusion Criteria

1. History of COVID-19 infection.
2. History of being treated or is currently being treated for any type of Malignancies or other co-morbid conditions that may result in protocol non-compliance.
3. Currently or in the past three months was treated with any type of Immune suppression medication (including chemotherapy, immunomodulatory drugs, biological agents that affect the immune system, any immunosuppressive drug such as corticosteroids).

4. Received in the past 4 months monoclonal antibodies of any type.

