#### **5.5.3 Withdrawal/Discontinuation Criteria**

All subjects should be encouraged to remain in the study through the entire follow up. However, if a subject decides to discontinue study participation, the reason for discontinuation must be recorded in the medical record and the Case Report Form (CRF). Subjects who discontinue participation prematurely will be included in the analysis of results (as appropriate) but they will not be replaced in the enrollment of total study subjects.

Every attempt must be made to have all subjects complete the follow up visit schedule. A subject will not be considered lost-to-follow up unless all efforts to obtain compliance are unsuccessful.

Discontinuation in the study will be if the antibody result at enrollment visit shows the participant already had the disease.

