## 5.9 Laboratory testing

From each HCW at each visit the following tests will be performed:

- The Platelia SARS-CoV-2 Total Ab assay by Bio rad, is a semi-quantitative in vitro diagnostic test, in a one-step antigen capture format, for the detection of IgM/IgA/IgG antibodies to the SARS-CoV-2 in human serum and plasma (EDTA, heparin, ACD or citrate) specimens. This assay will be performed at SMC virology laboratory (head- [name]).
- Antibody profiling of blood and nasal and mouth samples will be tested using antigen microarrays, this will be performed by using chip antigen microarrays spotted with various coronavirus antigens, as well as antigens of other common respiratory pathogens. This assay will be performed at [name] laboratory at Ben-Gurion University of the Negev.
- On select samples from each visit neutralization assays for SARS-CoV-2 virus variants will be performed. Each sample selected will be tested for its ability to inhibit infection of target ACE2-expressing cells by reporter pseudoviruses that express the spike protein of either Delta or Omicron Variant of Concern. This assay will be performed at [name] laboratory at Ben-Gurion University of the Negev.
- Blood samples for PBMC'S will be stored at [name] laboratory at Ben-Gurion University of the Negev for future research.

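### One unconfirmed positive N serology at any monthly draw counts as a primary event, which pulls the booster effect toward no effect by an amount set by an assay specificity the protocol does not give

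*Protocol*

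**What the plan says.** The Protocol Summary, section 5.2.1 and section 6 define the primary event in the same terms; section 5.2.1 reads "any type of COVID-19 infection as confirmed by PCR testing or positive serology for N antigen during the follow up period" and section 6 reads "COVID-19 infection as confirmed by PCR testing or positive serology for N antigen during the follow up period". The two routes are joined by 'or', so a positive N serology result is itself the confirmation. None of these places asks for a second positive, a rise from the worker's own enrolment value, or agreement with another test.

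Section 5.9 applies the assays to everyone at every visit: "From each HCW at each visit the following tests will be performed". The schedule in 5.3 shows blood at enrolment and then at "Month 1 Month 2 Month 3 Month 4 Month 5 Month 6", which is six post-enrolment draws. The Visit 2-6 heading in 5.8.2 could be read as five. The named kit "is a semi-quantitative in vitro diagnostic test, in a one-step antigen capture format". No specificity or cut-off is given, and 5.9 does not say which assay supplies the N result.

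At entry, 5.5.2 excludes "History of COVID-19 infection", and 5.5.3 adds: "Discontinuation in the study will be if the antibody result at enrollment visit shows the participant already had the disease". That sentence names neither the N antigen nor a threshold.

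**The concern.** Each uninfected worker has up to six chances to be called infected by one stray result. The planned infection rates are low, so even a small false-positive rate can make up a sizeable part of the events. The effect is largest in the boosted group, where true events are fewest.

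If the error rate is similar in both groups, and nothing in the protocol suggests otherwise, the false events dilute the contrast. Protection is understated and infection rates are overstated in both groups. The enrolment test helps by removing workers who are persistently reactive. It does not remove those who sit just below the cut-off and may cross it later.

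**Working it through.** **Inputs from section 6.** Monthly infection risk r is 0.025 (not boosted) and 0.010 (boosted); 60% choose the booster (600 v 400 of 1000); one-sided alpha is 0.025; loss is 10%; switching is 15%. Follow-up is 6 months (5.10), with six draws (5.3).

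**Assumed, not in the documents.** Per-draw specificity is 99.0% to 99.9%, with f = 1 − specificity, equal in both groups.

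**Plan without false positives.**
- Six-month risk: 1 − 0.975^6 = 14.1% and 1 − 0.99^6 = 5.9%.
- HR = ln(0.99)/ln(0.975) = 0.397.
- With 10% loss and 15% switching, about 83 events are expected (50 and 33).
- Schoenfeld power: Φ(√(83 × 0.6 × 0.4) × |ln 0.397| − 1.96) = Φ(4.12 − 1.96) = 98.5%. The stated 80.0% is therefore not reproduced. That is a separate matter, but it bears on how much power there is to lose.

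**Independent draws.** The chance of at least one false positive in six draws is 1 − (1 − f)^6. The observed monthly risk is 1 − (1 − r)(1 − f), and HR = ln(1 − risk boosted)/ln(1 − risk not boosted).

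At 99.0% specificity the monthly risks are 1 − 0.975 × 0.99 = 0.03475 and 1 − 0.99 × 0.99 = 0.0199. So HR = ln(0.9801)/ln(0.96525) = 0.02010/0.03537 = 0.57.

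| Assumed specificity | False positive in 6 draws | Observed 6-month risk, not boosted v boosted | HR | Excess share of boosted-group events |
|---|---|---|---|---|
| 99.0% | 5.9% | 19.1% v 11.4% | 0.57 | 48% |
| 99.5% | 3.0% | 16.6% v 8.6% | 0.50 | 32% |
| 99.8% | 1.2% | 15.1% v 7.0% | 0.44 | 16% |
| 99.9% | 0.6% | 14.6% v 6.4% | 0.42 | 9% |

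The excess share is (observed − 5.9%)/observed, computed before rounding. Five draws give the same HRs, because the monthly risks do not change.

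**Correlated draws, enrolment positives removed.** This was simulated with normally distributed noise and a cut-off set to the single-draw specificity. Anyone above the cut-off at enrolment was removed. Infections were taken to turn positive at the next draw and stay positive, with no switching or loss. With 50-75% of the noise variance stable within a person, the boosted/non-boosted rate ratio is about:
- 0.49-0.54 at 99.0%
- 0.46-0.48 at 99.5%
- 0.43-0.44 at 99.8%
- 0.41 at 99.9%

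Weaker correlation moves these toward the independent-draw column.

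**Effect of confirmation.** Requiring two consecutive positives in the same model brings the rate ratio back to about 0.40-0.42. It cuts the event rate in uninfected workers to about 0.5% or less. These runs did not count events first seen at Month 6, so they do not test any fallback rule for that visit.

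**Power with unconfirmed positives** (independent draws, 10% loss, 15% switching): 97.9% at 99.9% specificity, 97.2% at 99.8%, 94.5% at 99.5% and 88.9% at 99.0%. With five draws at 99.0% it is 83.8%. It drops to 76.4% with six draws only when specificity falls to 98%.

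**The case against.** **Is this left to the SAP?** Confirmation algorithms and cut-offs are often set in an SAP or laboratory manual, and neither is shown here. That would answer a missing detail. But the protocol states the event rule itself, three times, and under that rule one positive result suffices.

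**Is the size known?** It is not. Specificity is assumed throughout. At 99.9% the effect is small: about 58% apparent protection instead of 60%. Describing the kit as semi-quantitative says how it reads out and is not evidence of poor specificity. A reader might infer from the 99.0% row that about half of the boosted group's events would be false. The documents do not support that, because the figure needs both that specificity and independent draws. The enrolment screen makes independence the less favourable assumption.

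**Is the entry test the same test?** A reader might take the entry and event cut-offs to be identical. The protocol does not say so. That the enrolment result is an N result at the same cut-off is a reasonable inference, since all participants have had three vaccine doses and the outcome uses N serology.

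**Does it endanger the trial's conclusion?** A reader might infer that the superiority test is at risk. It is not over this range. Bias toward no effect is conservative for superiority, and on the stated inputs power remains above 80% at 99% specificity or better.

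**Does confirmation cost sensitivity?** It does to some extent. The simulation assumed that infections stay positive, so it cannot measure the loss. Repeating the same assay on the same serum would also not remove a cross-reaction specific to that sample, and a microarray check would be circular if the microarray produced the first result.

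**Conclusion.** The point holds for the effect estimate. The primary endpoint accepts any single positive N serology in a series of monthly tests, and at the planned infection rates this pulls the hazard ratio toward 1 and inflates the infection rates in both groups. Over an assumed specificity of 99.0% to 99.9%, a true ratio of 0.40 would appear as 0.57 to 0.42 with independent draws. It would appear as roughly 0.54 to 0.41 with enrolment positives removed and correlated noise.

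This rests on an undocumented specificity, a similar error rate in both groups, and the inference that enrolment removes N-positive workers. The direction is firm under these assumptions, and the size is not: it ranges from negligible to a substantial understatement of protection. It does not threaten the superiority claim on the stated inputs. It should be corrected because the size of the protection is what the study sets out to estimate.

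**What to change.** In 5.2.1, the Protocol Summary and section 6:
- Define a serology-only event as N-negative at enrolment followed by an N-positive draw, confirmed by a positive N result at the next scheduled draw. Date the event at the first positive draw.
- Where there is no later draw, confirm with a different N assay on the same visit's sample. The planned microarray would serve if it is not the source of the first result. Report how many events were confirmed this way.
- State that a positive PCR needs no confirmation.
- Add two sensitivity analyses: one counting all single positives, and one counting PCR-confirmed events only.

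**Cost.** This is mainly wording. The monthly draws, the microarray and the frozen serum are already planned, so no visit or sample is added, though a small amount of repeat laboratory testing may be needed. Some true serology-only infections will be lost, mainly those first seen at Month 6 or with rapid antibody decline. The single-positive analysis keeps them visible.
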